LEV 101-D-022521

NCT04857320

A Physician-Initiated Multiple-Dose, Single Period, Phase 0-I Dose Ranging Study to Examine Leveller™ HypoSpray Human Insulin Adult Healthy Volunteer Patients

Protocol No.: LEV 101-D-022521
ClinicalTrials.gov Reference NCT04857320

Criteria for evaluation: Statistical Analysis Plan

[figure not shown]
21st APRIL, 2021

Version 1.3

SPONSOR: Langford Research Institute

Principal Investigator: [name], D.O., M.P.H.

Approved by Langford Research Institutional Review Board April 21st, 2021

AMENDMENTS:

1.	2.	3.	4.
----	----	----	----

The information in this document contains trade secrets and commercial information that are privileged or confidential and may not be disclosed unless such disclosure is required by applicable laws and regulations. In any event, persons to whom the information is disclosed must be informed that the information is privileged or confidential and may not be further disclosed by them. These restrictions on disclosure will apply equally to all future information supplied to you, which is indicated as privileged or confidential. Copyright 2020 Transdermal Delivery Solutions Corp dba HypoSpray Pharma.

Criteria for evaluation: Statistical Analysis Plan	
Pharmacokinetics
 
Primary pharmacokinetic variables
 
The primary pharmacokinetic variables include: the reduction of serum glucose from baseline and at typical post prandial spikes and the amount of insulin necessary to accomplish this reduction. In addition to 90% confidence intervals, the data will be summarized by medians, and maximum and minimum values. The elimination half-life of Insulin will be compared using non-transformed data and parametric techniques. Averages for the serum glucose and Post-prandial excursions will be compared against averages for experimental periods.

---	---

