| Main Criteria for Inclusion | 
 
1. Healthy Adult Males
 
2. 20 and 60 years of age, inclusive.
 
3. The subject has a serum protein A1C of less than 6.
 
4. The subject is willing and able to read, understand the Subject Information Sheet and provide written informed consent.
 
5. The subject has a body mass index (BMI) within 18-50 kg/m^2.
 
6. The subject is in otherwise good health as determined by medical history and physical examination.
 
7. The subject is a non-smoker.
 
8. The subject must agree to continue with daily serum glucose testing by means of a wearable blood glucose for the pharmacokinetic assessments.
 
9. The subject is willing and able to comply with all testing and requirements defined in the protocol.
 
10. The subject is willing and able to return to the study site for all visits.
 
 |

|  |  |
|--|--|
| Main Criteria for Exclusion:        | 
 
1. The subject has any relevant deviations from normal other than blood glucose in physical examination, electrocardiogram (ECG), or clinical laboratory tests, as evaluated by the investigator.
 
2. The subject has had a clinically significant illness within 30 days preceding entry into this study.
 
3. The subject has a history of significant neurological, hepatic, renal, endocrine, cardiovascular, gastrointestinal, pulmonary, or metabolic disease.
 
4. The subject has a known allergy or history of hypersensitivity to Human Insulin or similar modified Insulin compounds.
 
5. The subject has used any prescription medication that may interfere with the evaluation of study medication.
 
6. The subject has donated or lost a significant volume of blood (>450 mL) within four (4) weeks of the study, and their Haemoglobin concentration and hematocrit have not returned to within 5% of normal.
 
7. The subject has a history of substance abuse or a current positive urine drug screen or urine alcohol test.
 
8. Alcohol consumption greater than community norms (i.e. more than 21 standard drinks per week for males).
 
9. Subjects who have received an investigational drug or have used an investigational device in the 30 days prior to study entry
 
 |

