| Concomitant Medication Restrictions | The intake of any medications (OTC or prescription) will be vigorously discouraged except as required to maintain health.  |
| Total expected number of subjects   | Sufficient volunteers will be recruited so as to obtain 5 completed subjects. Up to two additional subjects may be added.  |

|                   |  |
|-------------------|--|
| Study Drug | The investigational medicinal product is Human Insulin (Leveller HypoSpray L). Three dose ranges will be assessed: administered via sprays from a syringe. Doses will be calculated from what the literature reports is the low end of Healthy Volunteer Insulin Sensitivity. The 3 doses will be 0.075 IU/KG body weight, 0.1 IU/KG Body weight and 0.15 IU/KG Body Weight. This will result in dose ranges of 5 to 20 IUs. |
|-------------------|--|

|                                 |  |
|---------------------------------|--|
| Randomization            | Subjects will not be randomized. Sites of application: applied topically to the neck/chest arm, thigh area or inner aspect of a forearm.   |
| Dosage                   | Patients will receive dosing from the investigator and document blood sugar with a wearable Continuous Glucose Monitor (Libre 2) and will be dosed for 3 days. The monitor will be worn for 24 hours before the first dose and longer if available up to 7 days before beginning the study routine and 3 days after and receive the study drug via topical application for three days.   |
| Criteria for evaluation: | 
Pharmacokinetics
 
Primary pharmacokinetic variables
 
The primary pharmacokinetic variables include: the reduction of serum glucose from baseline and at typical post prandial spikes and the amount of insulin necessary to accomplish this reduction. In addition to 90% confidence intervals, the data will be summarized by medians, and maximum and minimum values. The elimination half-life of Insulin will be compared using non-transformed data and parametric techniques. Averages for the serum glucose and Post prandial excursions will be compared against averages for experimental periods.
  |

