| Patient Questionnaires                  |                      |                       |                           |                      | X                    |
| Adverse events                          |                      | X                     | X                         | X                    | X                    |

\* Normal pre and post meal and pre- and post bedtime Time Points as measured by the CGM

**A Physician-Initiated, Multiple-Dose, Single Period,  
Phase 0-I Dose Ranging Study to Examine  
Levvellor™ HypoSpray Human Insulin Adult  
Healthy Volunteer Patients  
VOLUNTEER DOCLOSURES**

Protocol No.: LEV 101-D-022521  
ClinicalTrials.gov Reference NCT04857320

[figure not shown]
21st APRIL, 2021

Version 1.3

SPONSOR: Langford Research Institute

Principal Investigator: [name], D.O., M.P.H.

Approved by Langford Research Institutional Review Board April 21st, 2021

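### Insulin elimination half-life is planned in men who secrete the same molecule, and the available text neither schedules an insulin concentration nor separates sprayed from secreted insulin

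*SAP*

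**What the plan says.** Under the primary pharmacokinetic variables, the SAP states: "The elimination half-life of Insulin will be compared using non-transformed data and parametric techniques". The protocol Synopsis (Criteria for evaluation) has the same sentence. Neither says what the half-life is compared with, how it is estimated, or whether any correction for endogenous insulin is made.

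The study drug is human insulin (Synopsis, Study Drug). On dosing: "The 3 doses will be 0.075 IU/KG body weight, 0.1 IU/KG Body weight and 0.15 IU/KG Body Weight". The inclusion criteria call for "Healthy Adult Males" and add "The subject has a serum protein A1C of less than 6"; significant endocrine or metabolic disease is an exclusion.

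For the untreated period the Synopsis describes glucose monitoring only: "The monitor will be worn for 24 hours before the first dose". The Flow Chart has a glucose profile row, with the footnote "Normal pre and post meal and pre- and post bedtime Time Points as measured by the CGM", and a general laboratory row at Visits 1, 2 and 4. It has no row for insulin concentration or C-peptide. C-peptide is also absent from the abbreviations and the SAP.

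The contents list names pharmacokinetic sampling at Visits 2 to 4 (5.1.2 to 5.1.4), a section on concentrations over sampling time (8.1) and an appendix on blood sampling for glucose and insulin (Appendix 5). The text under those headings is not available.

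**The concern.** A conventional insulin assay in these men measures sprayed plus secreted insulin. The half-life of that total is not the half-life of the drug. More sampling times, or analysis on another scale, would not separate the two sources.

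At stake is a named pharmacokinetic comparison in a dose-ranging study. A given endogenous floor distorts a small drug peak more than a large one, so identical kinetics at every dose could produce half-lives that differ by dose. With about five completers, such a pattern would be hard to recognise as an artefact.

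**Working it through.** **1. Can the Flow Chart yield a half-life?** A half-life of insulin needs serial insulin concentrations. The Flow Chart lists glucose from the continuous monitor and a general laboratory panel that does not name insulin. Glucose readings do not give an insulin half-life. On that schedule alone, the result is no estimate.

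**2. What if total insulin is sampled under the sections we cannot see?** The documents give no half-life, peak, endogenous level or sampling interval, so there is no plan figure to reproduce and every input here is an assumption:

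- true drug half-life 1 h
- drug-derived peak C0 = 20 or 40 uU/mL
- constant endogenous floor E = 5 to 10 uU/mL
- samples every 0.5 h; no absorption phase; no meal

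Model: C(t) = C0 × 0.5^t + E, with t in hours. Fit: regress ln C(t) on t; apparent half-life = ln 2 / (−slope).

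| C0 | E | E/C0 | fit over 0-4 h | fit over 2-4 h |
|---|---|---|---|---|
| 40 | 5 | 0.125 | 1.54 h | 2.00 h |
| 20 | 5 | 0.25 | 2.00 h | 2.96 h |
| 40 | 10 | 0.25 | 2.00 h | 2.96 h |
| 20 | 10 | 0.50 | 2.87 h | 4.85 h |
| either | 0 | 0 | 1.00 h | 1.00 h |

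The result depends only on E/C0, because multiplying the whole curve by a constant leaves the log slope unchanged. The bias is upward in every row with a floor. It vanishes when the floor is removed.

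**3. Could it look like a dose effect?** The doses span 0.15 / 0.075 = 2-fold. Assume that the drug peak is proportional to dose and that E = 7 uU/mL at both doses:

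- C0 = 20: slope −0.2945 per h; 0.6931 / 0.2945 = 2.35 h
- C0 = 40: slope −0.4017 per h; 0.6931 / 0.4017 = 1.73 h

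The true value is 1 h in both. The gap of about 0.6 h comes entirely from the floor.

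**4. Do other assumptions change the direction?** A second set used samples every 15 min over 0-180 min, with a constant floor given as a percentage of the drug peak and no meal:

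| true half-life | floor 10% | floor 25% | floor 50% |
|---|---|---|---|
| 30 min | 55 min | 83 min | 125 min |
| 60 min | 78 min | 103 min | 143 min |
| 90 min | 109 min | 136 min | 180 min |

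Every entry exceeds the true value.

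**5. A meal inside the window.** Add to the step 2 model, with E = 7, a triangular surge of 40 uU/mL from 1.0 to 4.0 h peaking at 2.5 h. The 0-4 h fit becomes 3.25 h (C0 = 40) or 8.36 h (C0 = 20), and the concentrations rise in mid-window. Letting E run from 5 to 10 widens this to 2.9 to 11.0 h. These values depend heavily on the assumed size and timing of the surge, and the documents do not say when insulin would be drawn relative to meals. They show only that a log-linear decline may not exist.

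**The case against.** The strongest reply is that the sampling detail lies in text we do not have. Sections 5.1.2 to 5.1.4, Section 8.1 and Appendix 5 are where sampling times, fasting state and assays would be set out. The Flow Chart is a weak guide to insulin assays, since it omits insulin sampling that the contents list names. This stands. The finding is that the available text states no separation, not that the full protocol lacks one. The SAP, however, does set out the half-life analysis, and it states no correction.

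A reader might infer that following the plan gives a wrong number. The documents do not support that: the Flow Chart schedules no insulin concentration, so as it stands it gives no number. The bias arises only if total insulin is sampled and left uncorrected.

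A reader might also take the meal footnote as showing that insulin is drawn around meals with no fasted period. The footnote belongs to the glucose profile row and describes monitor readings. It does not speak to insulin sampling.

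The magnitude is wholly assumed, and the model has no absorption phase although the product is transdermal. That stands too. The mechanism and the upward direction under a constant floor are shown; the size in this trial is not. Glucose lowering may also change secretion by dose, but that was not modelled. The dose pattern in the working arises from a fixed floor alone.

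Finally, little rests on half-life. The primary objective is glucose lowering and dose response, and the secondary is tolerability. The listed primary variables begin with "the reduction of serum glucose from baseline and at typical post prandial spikes" and add the insulin amount needed. Half-life is in neither place. This is accepted and limits the severity.

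**Conclusion.** The concern holds in a conditional form. The Synopsis and SAP name a quantity that the described design cannot deliver. The Flow Chart provides no insulin concentration from which to derive it, and if total insulin is sampled elsewhere, no stated step isolates the drug.

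In that second case, under a constant endogenous floor, the uncorrected half-life is biased upward: 1.5 to 2.9 h for an assumed true 1 h over a 0-4 h window. It could also falsely differ between doses, at 2.35 h against 1.73 h for a two-fold peak difference at a floor of 7 uU/mL. These figures rest on assumed values for half-life, peak, floor and sampling interval, and are not estimates for this trial.

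This should be fixed. Calling it critical would overstate it: the glucose objective is unaffected, and no stated decision depends on half-life.

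**What to change.** Delete the elimination half-life sentence from the Synopsis (Criteria for evaluation) and from the SAP, and limit the claim to the glucose response. This is a one-sentence edit in two places. The cost is one fewer stated variable; visits, dosing and the listed primary variables do not change.

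If the sponsor keeps half-life, the SAP should say that it is computed only on concentrations corrected for endogenous insulin measured concurrently, for example through C-peptide in the same samples, and should give the correction formula. Subtracting an untreated-day profile is not enough by itself, because dosing may change secretion. The SAP should also name the comparison and state that half-life is reported as not estimable where the corrected curve shows no log-linear decline. This route costs more: an extra assay and, unless the unavailable sections already provide them, scheduled insulin samples, in 5 to 7 men. Deletion is the proportionate choice.
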